Study protocol

Official Title: Effect of Natural Food on Gut Microbiome and Phospholipid Spectrum of Immune Cells in COVID-19 Patients

NCT number: NCT05970861

Document date: The 1st of October, 2024

Main Investigator: [name]., M.D.

Central Contact Backup (Project Manager): [name]

Study Officials:

[name].

[name]

[name]

[name].

Keywords: COVID-19, gut microbiome, antiphospholipid antibodies, rehabilitation, food products

Study Description

Brief Summary:

The efficacy of natural foods such as freeze-dried mare's milk (Saumal) in post-COVID syndrome therapy has not been studied. The literature review has shown that researchers have focused more on evidence-based medications and less on natural products. Some raw foods, such as freeze-dried mare's milk, contribute to forming complete immune complexes and have antioxidant, membrane stabilizing, and antiviral effects.

The use of Saumal proved its effectiveness in patients suffering from chronic hepatitis C. After 4 weeks of using freeze-dried mare's milk, the biodiversity of the intestinal microbiome was increased. The content of bacteria secreting short-chain fatty acids also increased.

The study aims to confirm these effects at the gene level in patients who underwent COVID-19. This study will allow us to develop a highly evidence-based component of rehabilitation therapy in patients after COVID-19.

Detailed Description:

The study consists of three stages.

Stage I. Randomized division of 75 patients under study into a main group of 38 patients receiving Saumal for 4 weeks and a control group of 37 patients not receiving Saumal. All respondents have suffered from COVID-19 in the last 6 months. At the moment of the research, all patients will be staying in rehabilitation centers in Almaty City.

The study's biological material will be collected from the respondents (gut microbiome, antiphospholipid antibodies, biochemical blood analysis (glucose, ALT, AST, uric acid, TAGs, alkaline phosphatase)).

Stage II. The main group will be given Saumal for four weeks, after which the gut microbiome, antiphospholipid antibodies, and biochemical blood analysis will be collected from both groups again. This will allow us to assess the impact of freeze-dried mare's milk on the condition of the gut microbiome, antiphospholipid antibodies, and biochemical blood analysis.

Stage III. Data analysis.

1. Based on the results of gut microbiome sequencing, ELISA (antiphospholipid antibodies), and biochemical blood analysis in the main and control groups, we determine the dynamic changes of those parameters during COVID-19 rehabilitation.
2. According to the results, the effectiveness of Saumal itself regarding these 2 parameters will be evaluated.
3. Develop recommendations and an algorithm for patient management after COVID-19 to prevent complications.

Study Design

Study Type: Interventional

Primary Purpose: Treatment

Interventional Study Model: Parallel Assignment

Number of Arms: 2

Masking: None (Open Label)

Allocation: Randomized

Enrollment: **60 patients.** Originally, we planned to include 38 patients in the main group and 37 in the control group. Overall, these groups were evenly divided, with 30 patients in each group.

Arms and Interventions

Arms	Assigned Interventions
Experimental: Main Group Patients who had suffered from COVID-19 in the six months before the start of the study. Patients will receive Saumal (freeze-dried mare milk) for four weeks.	Dietary Supplement: Freeze-dried Mare Milk (Saumal) Freeze-dried Mare Milk (Saumal) is frequently reported for having therapeutic and dietary properties associated with specific chemical composition and certain physical properties of the product. It contains a total of about 40 biologically active components, the most important of them vitamins A, C, B1, B2, B6, and B12, amino acids, enzymes, and trace elements (low molecular weight peptides, lactalbumins, and globulins). Saumal will be administered to patients at a dose of 25 grams of dry powder per 200 ml of water, 2 times a day, 30 minutes before the meal, for 4 weeks.
No Intervention: Control Group Patients who had suffered from COVID-19 in the six months before the start of the study. There will be no intervention.	

Eligibility

Minimum Age: 18 Years

Maximum Age: 75 Years

Sex: All

Gender Based: No

Accepts Healthy Volunteers: No

Inclusion Criteria:

Age 18 years and older;

Patients in rehabilitation after COVID-19;

Signed informed consent;

Presence of patient's history of COVID-19, reliably established by PCR+ /presence of IgG/ diagnosis of coronavirus pneumonia on Computer Tomography based on discharge from hospital or outpatient records.

Exclusion Criteria:

Chronic inflammatory bowel disease;
Gut microbiota transplantation;
Chronic pancreatic disease, period of exacerbation;
Liver cirrhosis, Metavir stage 3-4;
Any disease in the decompensation stage;
Neuralgic and psychological disorders that interfere with the study;
Cancer;
Non-transportable patients;
Patients who do not reside in Almaty;
Patients who have refused to participate in the study.

Examined for eligibility - 76 people;

Confirmed eligible - 60 people. According to our strict exclusion criteria, we had to remove 16 people [8 – oncological patients, 5 – moved house, 3 patients refused to participate];

Included in the study - 60 patients;

Completing follow-up and analysed - 60 patients.

Statistical Analysis Plan

Gut microbiota:

IBM SPSS ver. 23.0 (Chicago, IL, USA) was used to determine the statistical significance of the obtained data. All the indicators were verified for compliance with the law on normal distribution. If the variables obeyed this law, the Student's paired t-test was applied to determine statistical significance between the values before and after milk intake. Otherwise, the Wilcoxon sign rank criterion was used.

A single-factor analysis of variance was employed to verify the effect of administering freeze-dried mare's milk, which could potentially affect the indicators of gut microbiota.

Antiphospholipid antibodies:

The 95% confidence interval for aPL value was calculated for both median and mean. The confidence interval for the latter one was calculated in the descriptive statistics menu in IBM SPSS ver. 23.0 (Chicago, IL, USA).

It is necessary to find the value of the confidence coefficient (Student's criterion (t)) in the table of critical t-values, considering the total number of respondents (n) to find out a confidence interval for the median with a given confidence probability (p). After that, the calculation of the natural integer number (C) is needed for such a probability value: $C_p = (n/2 - t(p) \sqrt{n}/2)$. The lower confidence limit for the median is $X (C_p)$, where X is the ordinal number of the value in the ranked variation series corresponding to the lower boundary of the confidence interval. The upper confidence limit for the median is $X (n + 1 - C_p)$, where X is the ordinal number of the value in

the ranked variation series corresponding to the upper boundary of the confidence interval.

If the normal distribution law is followed, the Student's paired t-test was used to determine statistical significance between values before and after freeze-dried mare's milk. If not, the Wilcoxon sign rank criterion was used for intergroup comparison. One-way analysis of variance (ANOVA) was used to determine the relationship between the mare's milk prescription factor and aPL levels in both groups.

Quality of life:

IBM SPSS ver. 23.0 (Chicago, IL, USA) was used to determine the statistical significance of the obtained data. All the indicators were verified for compliance with the law on normal distribution. If the variables obeyed this law, the Student's paired t-test was applied to determine statistical significance between the values before and after milk intake. Otherwise, the Wilcoxon sign rank criterion was used.

A single-factor analysis of variance was employed to verify the effect of administering freeze-dried mare's milk, which could potentially affect the quality-of-life scores.

Results section

Gut microbiota analysis.

In the main group, after taking freeze-dried mare's milk, there was a decrease in the content of bacteria phyla Bacteroidetes, Proteobacteria, Verrucomicrobia and Chloroflexi (by 3.03%, 2.83%, 0.47% and 0.16, respectively), and an increase in the content of bacteria phyla Nitrospirae, Tenericutes, Cyanobacteria, Spirochaetes, Euryarchaeota, Actinobacteria and Firmicutes (by 0.02 %, 0.05%, 0.15%, 0.17%, 0.24%, 1.42% and 7.62%, respectively).

The Fusobacteria phylum was absent according to the results of mare's milk intake in all respondents. The Elusimicrobia phylum, on the contrary, was present in some respondents as a result of therapy.

Attention is also drawn to the presence of the Synergistetes phylum, which was absent in the control group both before and after therapy. Moreover, the difference between the Firmicutes, Proteobacteria, Chloroflexi, Cyanobacteria and Synergistetes phyla was statistically significant (Table 1).

Table 1. The percentage terms of all phyla of the gut microbiota in the main group before and after taking freeze-dried mare's milk (CI - confidence interval).

Phylum name	Before	After	95% CI (t-student)	p (t-student)
Bacteroidetes	32,32%	29,43%	-0,01; 0,07	0,178
Firmicutes	45,31%	51,87%	-0,09; -0,02	0,001
Proteobacteria	9,25%	6,52%	0,1; 0,28	<0,001
Actinobacteria	3,75%	4,9%	-0,15; 0,14	0,951
Euryarchaeota	1,28%	1,52%	-0,42; 0,1	0,204
Verrucomicrobia	1,29%	0,83%	-0,09; 0,32	0,223
Chloroflexi	0,23%	0,07%	0,04; 0,28	0,011
Cyanobacteria	0,16%	0,31%	-1,95; -0,17	0,028
Spirochaetes	0,08%	0,25%	-0,51; 0,17	0,324
Nitrospirae	0,01%	0,03%	-0,07; 0,02	0,235
Tenericutes	0,04%	0,09%	-0,2; 0,01	0,491
Fusobacteria	0,07%	0,00%	-0,05; 0,2	0,247
Elusimicrobia	0,00%	0,11%	-0,24; 0,02	0,109

Synergistetes	0,01%	0,09%	-0,14; -0,02	0,009
---------------	-------	-------	--------------	-------

In the control group, after taking freeze-dried mare's milk, there was a decrease in the content of bacteria phyla Bacteroidetes, Firmicutes, Chloroflexi and Cyanobacteria (by 2.5%, 0.4%, 0.07% and 0.07%, respectively), and an increase in the content of bacteria phyla Spirochaetes, Tenericutes, Fusobacteria, Verrucomicrobia, Proteobacteria, Euryarchaeota and Actinobacteria (by 0.005%, 0.01%, 0.04%, 0.24%, 0.26%, 0.48% and 3.56%, respectively).

The Nitrospirae and Elusimicrobia phyla were absent as a result of taking mare's milk in all respondents of the control group. At the beginning of therapy, some respondents were found to have bacteria of the Caldithrix phylum, which were absent during the repeated measurement. The Thermotogae phylum was found in several members of the control group during two measurements.

Moreover, the difference between the Actinobacteria and Chloroflexi phyla in the control group was statistically significant (Table 2).

Table 2. The percentage terms of all phyla of the gut microbiota in the control group after 2 stool tests (CI - confidence interval).

Phylum name	First test	Second test	95% CI (t-student)	p (t-student)
Bacteroidetes	32,27%	29,77%	-0,06; 0,08	0,754
Firmicutes	46,5%	46,1%	-0,06; 0,07	0,899
Proteobacteria	7,65%	7,91%	-0,1; 0,12	0,823
Actinobacteria	5,8%	9,36%	-0,46; -0,1	0,003
Euryarchaeota	0,39%	0,87%	-0,74; 0,24	0,209
Verrucomicrobia	1,72%	1,96%	-0,97; 0,85	0,871
Chloroflexi	0,10%	0,03%	0,002; 0,15	0,044
Cyanobacteria	0,41%	0,34%	-1,42; 1,89	0,728
Spirochaetes	0,007%	0,012%	-0,01; 0,004	0,324
Nitrospirae	0,01%	0,00%	-0,01; 0,02	0,324
Tenericutes	0,04%	0,05%	-0,12; 0,1	0,857
Fusobacteria	0,01%	0,05%	-0,13; 0,05	0,357
Elusimicrobia	0,03%	0,00%	-0,01; 0,07	0,090
Caldithrix	0,02%	0,00%	-0,01; 0,03	0,160
Thermotogae	0,02%	0,01%	-0,03; 0,06	0,454

The proportion of Bacteroidetes and Firmicutes in the gut microbiota is most significant. Summarizing their values in the main and control groups, we can see that their content increased in the former and decreased in the latter. Statistical analysis revealed a significant difference in the content of these phyla between the main group compared to the control group (Table 3).

Table 3. The percentage terms of Bacteroidetes and Firmicutes phylum in the main and control groups.

Main group			Control group		
Bacteroidete s+Firmicutes (before)	Bacteroidetes +Firmicutes (after)	p (Wilcoxon)	Bacteroidete s+Firmicutes (first test)	Bacteroidetes +Firmicutes (second test)	p (Wilcoxon)
77,63%	81,3%	0,026	78,76%	75,87%	0,213

To determine the effect of freeze-dried mare's milk on the gut microbiota at the phylum level, a one-factor analysis of variance was performed. A statistically significant relationship between such a factor as the administration of freeze-dried mare's milk was revealed in the Firmicutes, Elusimicrobia and Proteobacteria phyla (Table 4).

Table 4. The relationship between the use of prescribed freeze-dried mare's milk and indicators of gut microbiota at the phylum level.

Phylum name	p (One-way ANOVA)
Bacteroidetes	0,180
Firmicutes	0,048
Proteobacteria	0,043
Actinobacteria	0,186
Euryaychaeota	0,403
Verrucomicrobia	0,583
Chloroflexi	0,220
Cyanobacteria	0,280
Spirochaetes	0,340
Nitrospirae	0,143
Tenericutes	0,657
Fusobacteria	0,140
Elusimicrobia	0,044
Bacteroidetes + Firmicutes	0,037

Overall, the intake of freeze-dried mare's milk by post-COVID patients primarily contributed to an increase in the content of the sum of two major phyla of gut microbiota — Bacteroides and Firmicutes, with the latter being particularly significant. There is also a notable decrease in the number of bacteria from the Proteobacteria phylum in the main group, which includes representatives of pathogenic microflora.

Antiphospholipid antibody analysis.

29 out of 30 main group patients (96.67%) had normal IgM and IgG levels before taking freeze-dried mare's milk. In the case of the control group, aPL levels were normal in all respondents. The aPL levels were normal in patients of both groups after the second ELISA (Table 5).

Table 5. Antiphospholipid antibody scores of each patient in the main and control groups after two assays (aPL -antiphospholipid antibodies).

Main group		Control group					
aPL (before)		aPL (after)		aPL (first assay)		aPL (second assay)	

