After bringing the variables to the normal distribution, the statistical significance was found in the control group only (Table 8).

Table 8. Statistical analysis of normally distributed antiphospholipid antibody levels.

	95% CI	p-value (t-student)
Main group, IgM	-0,03; 0,11	0,185
Main group, IgG	-0,07; 0,11	0,726
Control group, IgM	0,04; 0,14	0,001
Control group, IgG	0,05; 0,15	0,0001

ANOVA was performed to determine the direct effect of the natural food product on the aPL values (Table 9). ANOVA did not reveal any statistical significances.

Table 9. Finding the effect of the freeze-dried mare's milk on the antiphospholipid antibody values (ANOVA - analysis of variance).

Antibody name	p (One-way ANOVA)
IgM	0,541
IgG	0,938

aPL values in almost all patients of both groups were ranged normally. The intersection of all confidence intervals of medians and means indicates the absence of statistical significance between these indicators. The results before and after bringing the aPL values to normal distribution differ greatly, especially for the IgM level in the main group. One-factor analysis of variance also showed the lack of significance of the studied factor. These several theses can explain the given results. First, initial aPL values could have been normalized over 6-9 months after COVID-19. Second, there were screening kits in the study. Therefore, the obtained results do not show the levels of specific phospholipids (phosphatidylcholine, phosphatidylethanolamine, aCL, anti- β 2-GP1, etc.). Third, the severity of COVID-19 was not considered as an inclusion criterion.

Quality of life analysis.

The quality of life of post-COVID patients in the main group statistically significantly improved in both physical and mental health components after using mare's milk. In the control group, there was no statistically significant change in quality-of-life indicators for both physical and mental health components. Even though the average score for the physical component in the control group is higher than in the main group, the level of statistical significance and the confidence interval of both groups allow us to conclude that freeze-dried mare's milk can have a positive effect on this indicator of the quality of life of post-COVID patients (Table 10).

Table 10. The average quality-of-life score in patients of the main and control groups.

	Quality-of-life components							
	Physical				Mental			

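### Tables 1 and 2 report only t-tests, although the SAP requires Wilcoxon for non-normal variables and five of the 29 rows cannot be normal at one visit

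*Combined protocol and SAP*

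**What the plan says.** **Rule.** The Statistical Analysis Plan, under Gut microbiota, says all indicators were checked for normality, then: "If the variables obeyed this law, the Student's paired t-test was applied to determine statistical significance between the values before and after milk intake". The alternative follows: "Otherwise, the Wilcoxon sign rank criterion was used". The antiphospholipid antibody (aPL) section has the same two branches, the second worded "If not, the Wilcoxon sign rank criterion was used for intergroup comparison". The SAP sections name no normality test and no transformation.

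**Gut results.** Table 1 (main group, 14 phyla) is headed "Phylum name Before After 95% CI (t-student) p (t-student"), and Table 2 (control group, 15 phyla) has the same two t-test columns. In the gut section Wilcoxon appears only in Table 3, for the sum of Bacteroidetes and Firmicutes. The text above Table 1 states: "The Fusobacteria phylum was absent according to the results of mare's milk intake in all respondents". The text above Table 2 reports Nitrospirae and Elusimicrobia absent in all control patients, and Caldithrix absent, at the second test. Main-group Elusimicrobia is printed as 0.00% before and described as appearing in some patients afterwards.

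**aPL results.** Above Table 8: "After bringing the variables to the normal distribution, the statistical significance was found in the control group only (Table 8"). Below Table 9: "The results before and after bringing the aPL values to normal distribution differ greatly, especially for the IgM level in the main group".

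**The concern.** The SAP makes the test depend on the data, so a reader needs to know which branch each row took. Tables 1 and 2 show one branch throughout, with no normality result reported, although some rows plainly belong to the other.

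This matters because seven within-group phylum changes are called significant on these t-tests: Firmicutes, Proteobacteria, Chloroflexi, Cyanobacteria and Synergistetes in the main group, and Actinobacteria and Chloroflexi in the control group. Several are low-abundance phyla, for which a handful of carriers may supply all the non-zero differences. There the t-test and the signed-rank test can disagree in either direction. For aPL, a transformation followed by a t-test is a third route that the SAP does not offer.

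**Working it through.** **Inputs.** n = 30 per group (Study Design: "Overall, these groups were evenly divided, with 30 patients in each group"), so 29 degrees of freedom. Intervals and p-values are from Tables 1, 2 and 8. A two-sided 5% level is assumed from the 95% intervals.

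**1. Are the printed figures paired t-tests at n = 30?** Take the mean difference as the interval midpoint, SE = half-width / 2.045, and t = midpoint / SE.
- Main Fusobacteria (-0.05; 0.20): midpoint 0.075, SE 0.125/2.045 = 0.0611, t = 1.23, p = 0.230. Rounding of the limits allows 0.201 to 0.261; printed 0.247.
- Main Elusimicrobia (-0.24; 0.02): midpoint -0.11, SE 0.13/2.045 = 0.0636, t = -1.73, p = 0.094. Rounding allows 0.081 to 0.109; printed 0.109.
- Control Nitrospirae, Elusimicrobia and Caldithrix: rounding allows 0.18 to 1.00, 0.084 to 0.211 and 0.136 to 0.613; printed 0.324, 0.090 and 0.160.

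All five fit a paired t-test. For main Fusobacteria and both Elusimicrobia rows the midpoint is close or equal to the raw percentage-point change (0.075 against 0.07; -0.11 against -0.11; 0.03 against 0.03), so these zero-heavy data appear to have been tested untransformed.

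**2. Does the rule send the five rows to Wilcoxon?** A variable that is zero in every patient is a constant and cannot pass a normality check, transformed or not. Four rows rest on stated absence. Main Elusimicrobia rests on the printed 0.00% and on the text's contrast with Fusobacteria.

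**3. How far can the two tests differ?** If k of 30 patients change by the same amount in the same direction and the rest do not change, t = sqrt(29k/(30 - k)). This is also the largest t that k non-zero differences can give. The exact signed-rank p, with zeros dropped and all signs alike, is 2/2^k.

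| k | t | t-test p | exact signed-rank p |
|---|---|---|---|
| 4 | 2.11 | 0.043 | 0.125 |
| 5 | 2.41 | 0.023 | 0.063 |
| 6 | 2.69 | 0.012 | 0.031 |
| 7 | 2.97 | 0.006 | 0.016 |

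The contrast depends on the exact version. At k = 4 with equal changes, the normal approximation has rank-sum mean 5 and tie-corrected variance 7.5 - 60/48 = 6.25, so z = 5/2.5 = 2.0 and p = 0.046.

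The disagreement can also run the other way. If main Elusimicrobia was zero in everyone before, all its non-zero differences share a sign, and six or more carriers give an exact p of 0.031 or less, against the printed 0.109.

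**4. Which significant rows could rest on few carriers?** Main Cyanobacteria (0.028) needs at least 5 non-zero differences and control Chloroflexi (0.044) at least 4. Synergistetes (0.009) and main Chloroflexi (0.011) need at least 7.

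**5. Are the intervals on the printed scale?** Some are not.
- Main Proteobacteria changes by 9.25 - 6.52 = 2.73 points (0.0273 as a proportion); the interval is 0.10 to 0.28.
- Control Actinobacteria changes by 5.80 - 9.36 = -3.56 points (-0.0356); the interval is -0.46 to -0.10.

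Both exclude the change on either scale. The log10 ratios of the means, 0.152 and -0.208, fall inside, which suggests a transformation in these tables too.

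**6. aPL.** Table 8 gives p = 0.185 and 0.726 in the main group and 0.001 and 0.0001 in the control group (IgM and IgG). Table 9, the ANOVA for the effect of the milk, gives 0.541 and 0.938.

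**The case against.** The strongest reply is that little of what the document concludes depends on the five rows. None is significant, so none is a false positive. The closing gut statement rests on Firmicutes, Proteobacteria and the Bacteroidetes plus Firmicutes sum. These are abundant phyla that may well have passed a normality check; the sum was tested by Wilcoxon (Table 3, p = 0.026), and Table 4 gives ANOVA results for all three (0.048, 0.043, 0.037). That stands.

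The figures for k = 4 and 5 assume equal changes, and no carrier counts are given. That stands too: they show what is possible, not what happened, and they cannot account for the Synergistetes or main Chloroflexi p-values.

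On aPL, the copy reviewed lacks the part that would hold Tables 6 and 7. A reader might infer that the transformation was never named, that no rule says which result counts, or that the choice was made after the results were seen. None of this can be shown: the missing part may deal with the first two, and nothing visible dates the choice. A reader might also infer that the transformation decides the aPL finding. The document's treatment conclusion is null, and the significant Table 8 rows are in the untreated group.

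None of this answers the conflict between the SAP's rule and the tests shown in Tables 1 and 2. That Table 3 uses Wilcoxon shows the test was available.

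**Conclusion.** The point holds as a departure from the SAP's own rule and a gap in reporting. All 29 rows (14 + 15) show t-tests only, and five of them should have gone to Wilcoxon. For the other 24 rows the documents do not show which branch the rule required.

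The effect on significance calls could go in either direction and cannot be computed without patient-level data. Among the seven significant changes, main Cyanobacteria and control Chloroflexi are those whose p-values as few as five or four carriers could produce. The documents do not support a claim that these rows are false positives, or that the main gut conclusion fails.

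For aPL, the visible text establishes only a step outside the SAP's two branches and the document's own remark that the results differ greatly. This affects within-group p-values.

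Assumptions: 30 complete pairs per group, two-sided 5%, exact signed-rank with zeros dropped, and a printed 0.00% for main Elusimicrobia meaning absent in all patients.

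**What to change.** - Name the normality test and apply it to the paired differences, which is what the paired t-test requires. This refines the SAP's rule, which checks the variables.
- Report Wilcoxon for every phylum and aPL measure that fails, including the five zero-heavy rows. Use exact p-values where few differences are non-zero, and give the number of carriers at each visit.
- Mark the test used and the scale of the interval for each row of Tables 1 and 2, and revise the list of significant phyla to match.
- Identify any transformation used in Tables 1, 2 and 8 and label it a sensitivity analysis. Base within-group aPL statements on the SAP's planned test.

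The cost is a re-run in the same software on data from 60 patients, plus table footnotes. Some nominally significant rows may be lost or gained.

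### The rank formula for the 95% confidence interval of the aPL median uses Student's t where a binomial or normal value belongs and gives no rounding rule, so at 30 per arm it yields a 98.4% or a 95.7% interval depending on how C is rounded.

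*Combined protocol and SAP*

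**What the plan says.** The rule is in the Statistical Analysis Plan, under Antiphospholipid antibodies.

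- Stated level: "The 95% confidence interval for aPL value was calculated for both median and mean".
- Critical value for the median interval: the analyst is to "find the value of the confidence coefficient (Student's criterion (t)) in the table of critical t-values, considering the total number of respondents (n").
- Lower rank: "the calculation of the natural integer number (C) is needed for such a probability value: $C_p = (n/2 - t(p) \sqrt{n}/2").
- Upper rank: "The upper confidence limit for the median is $X (n + 1 - C_p").

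C must be a whole number, but no rule is given for a C that is not whole. The plan does not say whether n is the arm size or the trial total. The Enrollment entry under Study Design says "these groups were evenly divided, with 30 patients in each group", and the participant counts before the plan give "Completing follow-up and analysed - 60 patients".

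The intervals are used in the Results section, under Antiphospholipid antibody analysis: "The intersection of all confidence intervals of medians and means indicates the absence of statistical significance between these indicators".

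**The concern.** An order-statistic interval for a median depends only on how many of the n observations fall below the true median. For continuous data that count is Binomial(n, 1/2), with mean n/2 and standard deviation √n/2, both known exactly. Student's t allows for a standard deviation estimated from the sample, and none is estimated here. The right multiplier is the normal quantile, as an approximation, or better no multiplier at all: ranks read directly from the binomial distribution.

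The larger t value pushes C down and the limits outwards. Because C must be whole, a small shift can move each limit by one full rank. With no rounding rule, two analysts following the plan on the same data can report different intervals, both labelled 95%. The labels matter because the aPL results treat overlap of intervals as evidence of no difference, and an interval wider than its label makes overlap more likely.

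**Working it through.** **Inputs**

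- Two-sided level 95% (Statistical Analysis Plan, Antiphospholipid antibodies).
- n = 30 per arm (Study Design, Enrollment), with all 60 analysed.
- Ranks C and n + 1 − C, where C = n/2 − q√n/2. The plan takes q from the t table.
- Standard quantiles: t = 2.045 on 29 df, z = 1.960.

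**Step 1: C at n = 30.** √30/2 = 2.739.

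- Plan's rule: C = 15 − 2.045 × 2.739 = 9.40. Entering the t table at 30 df (2.042) gives 9.41, which leads to the same ranks.
- Normal quantile: C = 15 − 1.960 × 2.739 = 9.63.

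**Step 2: exact coverage.** For ranks C and n + 1 − C, coverage = 1 − 2·P(Bin(30, ½) ≤ C − 1).

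| Ranks | One tail | Coverage |
|---|---|---|
| 9 and 22 | 0.00806 | 98.39% |
| 10 and 21 | 0.02139 | 95.72% |
| 11 and 20 | 0.04937 | 90.13% |

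Exactly 95% cannot be reached at n = 30. The 10th and 21st values are the narrowest symmetric pair with at least 95%.

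**Step 3: what the rounding rule does.**

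| Rounding of C | t (9.40) | z (9.63) |
|---|---|---|
| Down | 9, 98.39% | 9, 98.39% |
| Nearest | 9, 98.39% | 10, 95.72% |
| Up | 10, 95.72% | 10, 95.72% |

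The choice of t over z changes the ranks only under rounding to nearest. The switch occurs where C = 9.5, that is at q = (15 − 9.5)/2.739 = 2.008, and t on 29 or 30 df lies above it. So the plan's 95% is nearly met (95.72%) if C is rounded up and is not met as labelled (98.39%) under the other two conventions.

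**Step 4: width.** In 100,000 simulated samples of 30, the mean width of the 9th–22nd interval was 1.20 times that of the 10th–21st for normal data and 1.22 times for lognormal data.

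**Step 5: n = 60.** If n were the trial total, t = 2.001 (59 df) gives C = 30 − 2.001 × 3.873 = 22.25, and z gives 22.41. Any one rounding rule then gives the same rank for both: 22 (97.27%) to nearest or down, 23 (94.81%) up. With C = 22 the upper rank is 39, which does not exist in an arm of 30.

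**Step 6: the overlap criterion.** Two separate before and after intervals were simulated with n = 30, normal data and no true change. With no correlation between the two measurements they failed to overlap in about 0.4% of samples using ranks 10 and 21, and about 0.1% using 9 and 22. At correlation 0.5 both were about 0.05% or less. The overlap criterion is therefore far stricter than a 5% test with either pair of ranks.

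**The case against.** **Cause.** A reader might infer that Student's t by itself produces a 98.4% interval. The documents do not support that. With rounding down, z gives the same 9th and 22nd values; with rounding up, t gives the 10th and 21st. The missing rounding rule matters at least as much as the wrong critical value. This part of the objection stands in full.

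**What was reported.** A reader might also infer that the published median intervals are wrong as labelled. No median interval is visible in the text available for review, so the ranks used are unknown. This also stands: the defect lies in the stated rule, not in a demonstrated result.

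**Meaning of n.** Reading the total number of respondents as 60 leads to a rank that cannot exist in an arm. That is good evidence that the arm size was meant. It is loose wording to tidy up, not a separate error.

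**Direction and weight.** The adverse case is conservative: the interval covers more than it claims. The aPL conclusion also cites intervals for means, which come from SPSS, and the one-way ANOVA in Table 9 (p = 0.541 for IgM, 0.938 for IgG). Neither uses this formula, nor do the paired tests in Table 8. The stronger driver towards finding no change is the overlap criterion itself, as Step 6 shows, and correcting the ranks would not cure it. All of this limits the consequence. It does not make the formula right or its output unique.

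**Conclusion.** The rule is wrong as written on two counts: the critical value has no basis in this formula, and the rank is not determined because no rounding rule is given. At n = 30, rounding to nearest or down labels a 98.4% interval as 95%, an error rate of 1.6% where about 5% is implied, with an interval about 20% wider than the 10th–21st. Rounding up gives 95.7%, which is acceptable.

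This rests on n being the arm size, t taken at 29 or 30 df, and continuous data; the width figure comes from simulated normal and lognormal samples, not from trial data.

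It should not be read as showing that any aPL finding would reverse. The practical consequence is narrower: the intervals feed a statement of no significance drawn from overlap, and extra width favours that statement. Table 8 shows why this deserves care, since after normalisation it reports within-control changes at p = 0.001 (IgM) and p = 0.0001 (IgG), which overlap of separate intervals does not test.

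**What to change.** - Replace the t-based formula with exact binomial ranks. At 30 per arm the limits are the 10th and 21st ordered values; report the achieved level of 95.7%.
- State that n is the number of patients in the arm with a value at that assay.
- Recompute every aPL median interval on this rule, and state which ranks were used for those already reported.
- For change between the two assays, give an interval for the paired change, for example Hodges–Lehmann, and drop overlap of separate intervals as a criterion of significance.

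The cost is a sentence or two in the plan and a recalculation from data already in hand. No new data are needed.
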